- First, there is an urgent need to examine secondary distribution of HIVSS by women to male partners in **South Africa**. Few HIVSS studies have been conducted in South Africa which has very different epidemic and contextual factors (e.g., higher levels of IPV) versus Kenya and Malawi where most previous studies were conducted. In contrast to the higher acceptability of HIVSS reported by clients in Kenya and Malawi (17) some studies from South Africa indicate that acceptability may be low which could greatly limit HIVSS impact, while other studies indicate that acceptability may be high in South Africa (18). To our knowledge, no randomized controlled trials of the effectiveness of secondary HIVSS distribution have taken place among South Africa adults.
- Second, more research is needed to **validate partner HIVSS use and results** after distribution. A systematic review found that three strategies may be able to verify HIVSS results (supervision by a health provider, returning used kits, and electronic transmission of photographs), but evaluation and development of innovative strategies for verifying HIVSS use and results is urgently needed (19).

- Finally, prior trials of HIVSS have focused on primary outcomes of HIVSS uptake among partners. It is additionally and critically important to understand whether HIVSS strategies lead to **improved partner ART uptake** among newly diagnosed men.

COVID-19 and study implications. The Department of Health and PEPFAR partners, including BroadReach Healthcare, have continued to offer HIV testing, treatment and monitoring during the COVID-19 lockdown in South Africa as HIV services are essential health services. The team will continue to observe all Department of Health infection prevention and control methods. The proposed intervention is important during the COVID-19 lockdown as it is designed to promote HIV testing and case finding from home to improve linkage to treatment from the HIV+ partner.

3. Study Objectives:

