We will partner with BroadReach Healthcare, a PEPFAR partner in South Africa, to pilot test an innovative index partner HIVSS strategy in one urban and one rural public health clinic in the Nkangala district of Mpumalanga Province to evaluate **acceptability, barriers, and preliminary efficacy** of secondary HIVSS distribution in a randomized control trial enrolling women newly diagnosed with HIV or on ART. In the intervention arm, women will receive counselling on how to use HIVSS, how to encourage their male partner to screen, and 2 HIVSSs with HIVSS instructions and invitation to return for confirmatory testing. In the standard of care arm, index women will receive counselling on the importance of disclosure to their family and partner(s) and referral for HIV testing (per SA national guidelines). We will evaluate the following aims:

1. Conduct a mixed-methods survey with N=100 HIV+ women to assess perceived **acceptability and barriers** (including perceived safety, IPV) to secondary HIVSS distribution by women to male partners.
2. Test the **feasibility** and **preliminary efficacy** of secondary HIVSS distribution through a 1:1 randomized control trial in n=100 HIV+ women to assess, comparing standard of care to intervention arm:
 - a. % of index women who self-report that they gave the HIVSS or standard of care referral for testing to their male partner
 - b. % of male partners who either screened or tested for HIV assessed at 3 months after randomization (*primary outcome*)
 - i. Measured via options of: index or partner self-report, SMS/WhatsApp of a picture of the used HIVSS sent by partner or index, return of a used self-test to the facility by either the index or partner, and/or partner coming into facility for with an invitation for confirmatory testing or SOC counseling referral
 - c. % of male partners with a positive HIV screening/test result
 - d. % of newly diagnosed male partners who initiate ART within 3 months of diagnosis
 - e. % of those on ART with viral suppression after 6 months on ART (index and partners)
3. In the intervention arm, we will assess acceptability and barriers (including safety/IPV) related to HIVSS distribution or use via surveys with all intervention participants who return for the study endline survey and a convenience samples of n=20 male partners (n=10 men who used HIVSS and n=10 men who did not use HIVSS)

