Baseline survey: After consent, a trained interviewer/counselor will administer a brief 10-15 minute survey to n=100 WLHIV about socio-demographics (age, education, relationship status), knowledge of partner's prior HIV testing and status, willingness to distribute HIVSS to their partner(s), facilitators/barriers to HIVSS (17). A trained study staff will ask the survey questions in the local dialect using RedCap. Participants will receive an option to participate in the interview on the phone instead of returning to the health facility.

Randomization: Following the baseline survey, women will be randomized to receive a HIVSS or referral in a 1:1 ratio to the intervention or standard of care arm. Randomization will be performed using a random number table by participant ID, who will be provided with sealed randomization envelopes. The participants will open the envelopes sequentially.

Male partner contact: For women allocated to the intervention arm, the participant will be given a HIVSS to take home to their partner(s). The counsellors will give the participant two options for contacting their partners:

- The participant will contact their partner (via a telephone call or SMS) while in the counselling session to confirm the partner's participation and obtain permission to provide his contact details.
- The participant will ask the partner to contact the counsellor to confirm participation and provide his contact details. If the participant confirms that her partner consented to participate in the study, the counsellor will call him to request his consent over the phone and confirm that he is her partner (using his name and date of birth). The interviewer will read the consent form on the phone and send him a copy via SMS/WhatsApp or email.

Standard of care arm: In the standard of care arm, women will receive standard of care partner referrals for HIV testing, including counselling about disclosure and referral for her partner(s) to return to the facility for testing. They will complete an endline survey after ~3 months (or when they return for their next clinical visit, ART start, or drug pick up visit) to evaluate the uptake of partner testing, results, and safety, including IPV.

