Female partner endline survey (intervention arm): Study staff in the facility will conduct a brief 10 minute endline survey in all participants who return at 3 months (or when they return for their next clinical visit, ART start, or drug pick up visit) to report on primary outcomes including partner HIV testing, results and confirmatory testing. If the women do not return in 3 months, UCT staff will conduct the survey telephonically.

Male partner endline survey (intervention arm): Following the survey and counselling, we will ask female participants to ask their partner if he consents (verbally or via SMS/WhatsApp) that we can follow them up. Study staff will contact women who agree in 24-48 hours following the survey to speak with her partner or ask her to give the study phone number to call us to consent to participate in a brief survey. We will attempt to recruit 20 male partners from the intervention arm (n=10 who used the test and n=10 who did not use the test) to provide informed consent to participate in study survey to evaluate use of HIVSS, acceptability (including linking HIVSS to couples testing or disclosure), barriers and any reported harms or reactions over the phone. Male partners will be asked about what they liked about HIVSS, acceptability and ease of use.

Note: All surveys will be translated into isiZulu and back-translated into English to confirm accuracy prior to implementation.

Human Resources: We will train 1-2 BroadReach and DoH HTS counsellors to select the women, consent them and interview them (30-45 minutes) and then either allocate the HIVSS or counselling about importance of partner testing, depending on randomization. A BroadReach Manager will manage the quality of the study and ensure a timely reporting, and contact colleagues at UCT with problems/queries. A trained UCT research staff will conduct the follow up surveys telephonically with women who are unable to return to the facility. The research staff will also conduct interviews with men (n=20) for the endline survey.

Table 1. Pilot study timeline

	Nov	Dec	Jan	Feb	Mar	Apr	May
Mpumalanga Province, District and UCT HREC proposal submission, review and approval	X						
Train HTS counsellors and BR manager in pilot study SOPs, survey and procedures	X						
Develop RedCap survey and pre-test with staff	X						
Recruit and enroll n=100 WLHIV in the study (n=50/month)			X	X			
Baseline survey and eligibility screening (n=100 WLHIV)			X	X			

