Randomize n=100 WLHIV to intervention vs standard of care			X	X			
Deliver HIVSS and instructions to n=50 and referral counseling to n=50			X	X			
Follow up participants at ~3 months (to coincide with next clinical visit) to conduct endline survey and evaluate HIV testing uptake, results					X	X	X

(positivity) and linkage (telephonically and using health records)						
Study endline survey for n=20 partners in the intervention arm (telephonically)				X	X	X
Analysis and dissemination					X	X

Evaluation: We will evaluate the following outcomes in the study including:

1. % of index women who self-report that they gave the HIVSS or SOC counseling referral to their male partner
2. % of male partners who either screened or tested for HIV assessed at 3 months after randomization (primary outcome)
 - i. Outcome measured via: index or partner self-report, SMS/WhatsApp of a picture of the used HIVSS sent by partner or index, return of a used self-test to the facility by either the index or partner, and/or partner coming into facility for with an invitation for confirmatory testing or SOC counseling referral
3. % of male partners with a positive HIV screening/test result (case finding)
4. % of newly diagnosed male partners who initiate ART within 3 months of diagnosis
5. % of those on ART with viral suppression after 6 months on ART (index and partners)

4. Ethical considerations

The study protocol, informed consent form, all data collection tools, and other requested documents will be reviewed and approved by the University of Cape Town Faculty of Health Sciences Human Research Ethics Committee (UCT-HREC).

Informed consent

The study informed consent for the study and questionnaire are modelled after that used in previous studies and will be delivered in participants' home language by trained interviewers. The informed consent form (ICF) will be translated into isiZulu and back-translated into English to confirm accuracy. This study ICF details the purpose of the study, study procedures, and the risks and benefits to women that participants may encounter at the second study visit. We will ask women if they want to consent to give her partners' contact information (phone number), but this will not be required to join the study.

Here, study staff will emphasize to participants that:

- Participation is entirely voluntary, and their choice regarding participation will in no way influence the quality of routine medical care for mothers

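### Outcome 4 (partner ART start) takes its denominator and 3-month clock from an undefined diagnosis; if that means facility confirmation, kit-arm men who screen reactive but never confirm drop out of the linkage figure

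*Combined protocol and SAP*

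**What the plan says.** The Evaluation section lists five outcomes. Outcome 4 is the percentage "of newly diagnosed male partners who initiate ART within 3 months of diagnosis", and Aim 2d under Study Objectives uses the same words. Neither place says what makes a man newly diagnosed or which date starts the three months.

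The outcome just before it has a wider base. Outcome 3 is the percentage "of male partners with a positive HIV screening/test result (case finding"), so a reactive self-screen counts there without confirmation. The primary outcome likewise accepts either a screen or a test.

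The two arms reach a facility result by different routes. Women in the kit arm receive "2 HIVSSs with HIVSS instructions and invitation to return for confirmatory testing" (Study Objectives). Women in the standard-of-care arm receive counselling and "referral for her partner(s) to return to the facility for testing" (Study procedures, standard of care arm).

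The kit-arm endline survey asks women "to report on primary outcomes including partner HIV testing, results and confirmatory testing". Confirmation is therefore asked about, but no date is mentioned, and none of the five listed outcomes is a confirmation percentage.

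The background names "improved partner ART uptake" among newly diagnosed men as one of the gaps the study should address.

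**The concern.** A linkage percentage depends on who enters the denominator and when the clock starts. Here both hang on one undefined word, and the event it most naturally describes sits at a different point in each arm's pathway. In the standard-of-care arm the first positive result is a facility test, so positive result and diagnosis coincide. In the kit arm the first positive result is a home screen, and a facility visit must follow.

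If diagnosis means the result of that visit, two things happen in the kit arm only. Reactive men who never attend are not in outcome 4 at all, so their failure to reach ART does not lower it. Reactive men who attend late remain in outcome 4, but their three months start late.

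At stake is the pilot's answer on ART uptake, which is meant to inform a larger trial. The kit arm could match or beat standard of care on outcome 4 while a smaller share of its men with a positive result start ART. Two analysts could also report different percentages from the same data, each consistent with the text.

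**Working it through.** The protocol gives no expected rates, effect size, alpha or power, so there is no planned figure to reproduce. Every rate below is an assumption.

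**Step 1: which reading is natural.** Outcomes 2 and 3 join screening and testing explicitly. Outcome 4 drops that pairing and speaks of newly diagnosed men, in a pathway where the screen leads to an "invitation to return for confirmatory testing". This favours facility confirmation. It is an inference, because the text does not define the term.

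**Step 2: size of the denominator effect in the kit arm.**

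- c = share of men with a reactive screen who are confirmed at the facility
- a = share of confirmed men who start ART within three months of confirmation
- unconfirmed men are taken not to start ART

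Outcome 4 on the confirmed reading = a. ART start per reactive screen = a × c. Difference = a − ac = a(1 − c).

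| a (outcome 4 as read) | c | a × c | Difference, points |
|---|---|---|---|
| 0.80 | 0.50 | 0.400 | 40.0 |
| 0.80 | 0.90 | 0.720 | 8.0 |
| 0.90 | 0.50 | 0.450 | 45.0 |
| 0.90 | 0.75 | 0.675 | 22.5 |
| 0.90 | 0.90 | 0.810 | 9.0 |
| 0.95 | 0.50 | 0.475 | 47.5 |
| 0.95 | 0.90 | 0.855 | 9.5 |

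For a from 0.80 to 0.95 and c from 0.50 to 0.90 the difference runs from 8 to 47.5 points. It is zero at c = 1, and zero if diagnosis means the reactive screen. Standard-of-care men have no earlier screening step, so this term does not arise for them.

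**Step 3: the clock.** A man confirmed d months after his reactive screen can start ART up to d + 3 months after the screen and still count as within three months. With d = 2, that is 5 months. This matters only if ART starts are still being recorded then. Three months from any diagnosis made after randomisation already runs past three months from randomisation, so the roughly 3-month endline alone cannot always close the window. Table 1 names health records as a source for linkage but gives no cut-off date.

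**Step 4: counts.** With 50 women in the kit arm, one partner each, kit use of 50% to 90% and 10% to 30% of users reactive (all assumed), reactive men number from 50 × 0.50 × 0.10 = 2.5 to 50 × 0.90 × 0.30 = 13.5. Single men then move the percentage. Suppose 4 of 5 confirmed men start ART, or 80%. Adding one unconfirmed man gives 4/6 = 67%, and adding two gives 4/7 = 57%.

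**Step 5: what a comparison could show.** Even with all 50 women per arm as the denominator, power is low. The most favourable scenario tried assumed testing of 90% v 40%, 30% positive, everyone confirmed and a = 0.90. ART starts are then 0.90 × 0.30 × 0.90 × 50 = 12.15 v 0.40 × 0.30 × 0.90 × 50 = 5.4, and power is 42.5% at two-sided 5%. Any version of this outcome is an estimate to describe, not a test.

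**The case against.** The strongest reply is that the protocol never says a man is newly diagnosed only once he attends. Outcome 3 treats a positive screen as case finding, so the reactive screen could be the diagnosis. In that case nobody is dropped and the bias is zero. This stands as far as it goes: the firm finding is an undefined term, and the bias is conditional on the reading.

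A reader might also infer that men who confirm late are dropped. The definition does not do that; they stay in the denominator with a later start. They would be lost only if confirmation fell after data collection ended. Nor do the documents support saying that this is the step where self-screening most often loses men, because they give no rate of loss between screen and confirmation.

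The background frames its question as ART uptake among newly diagnosed men, so outcome 4 does match a stated aim. That is why the diagnosis-based figure should be kept. The confirmation step is not wholly out of sight either: outcome 2 accepts a partner's facility visit with the invitation as evidence of testing, and the numerators and denominators of outcomes 3 and 4 would let a careful reader reconstruct much of it. What is missing is a stated count and percentage.

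Finally, some unconfirmed reactive screens will be false positives. Keeping all of them as not on ART would then understate linkage among men who truly have HIV. This stands, and it is the reason to show both figures and not replace one with the other.

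**Conclusion.** The point holds as a definitional gap with a conditional bias. Diagnosis is undefined in outcome 4 and Aim 2d. On the natural reading, the denominator leaves out never-confirmed reactive men in the kit arm only, and the clock ignores the delay of those who confirm late. Linkage per reactive screen is then overstated by a(1−c), which is 8 to 47.5 points over the assumed ranges; on the other reading there is no overstatement. The full difference is lost linkage only if the unconfirmed men are truly infected and did not start ART elsewhere.

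The consequence is confined to ART linkage in a small pilot. The primary outcome and outcome 3 already count screens and are untouched. It is still worth correcting, because the protocol gives partner ART uptake prominence and the correction is cheap.

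**What to change.** 1. Define newly diagnosed and the date of diagnosis in the same way for both arms, in outcome 4 and Aim 2d.
2. Report by arm, as separate counts, men with a reactive screen or positive test, men with facility confirmation, and men who started ART.
3. Add ART start among all men with a first reactive screen or positive test, with the clock starting at that result. Keep unconfirmed men as not on ART unless records show otherwise. Present this beside the diagnosis-based percentage.
4. State the source and cut-off date for ART starts, since the window can outlast the endline.

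The cost is mainly tabulation. Confirmatory testing is already asked about at the kit-arm endline, but screen and confirmation dates may have to be added to the survey. The kit-arm figure will look less favourable, and false-positive screens will pull it down further, hence the two figures side by side. The new denominator is still formed after randomisation and the counts will be small, so the comparison between arms should be labelled descriptive.
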